### 3.2 Inclusion criteria

Patients eligible for inclusion in this early treatment protocol have to meet **all** of the following criteria:

1. Histologically or cytologically confirmed diagnosis of lung adenocarcinoma that demonstrates *ALK* rearrangement as detected by the approved FISH test (Abbott Molecular Inc), using Vysis breakapart probes (defined as 15% or more positive tumor cells); or the Ventana IHC test. Evidence of rearrangement by gene sequencing tests such as FoundationOne or Caris will also be seen as evidence of *ALK* abnormality and meeting eligibility requirement.
2. Patients with no prior *ALK*-inhibitor therapy will be placed in cohort A, those treated with one prior line of *ALK*-inhibitor (at any time) will enter cohort B.
3. Patients will not have any other curative therapeutic option, such as radiation or surgery.
4. WHO performance status 0-2.
5. Age  $\geq$ 18 years.
6. Patients must have recovered from all toxicities related to any prior anticancer therapies to  $\leq$  Grade 2 (CTCAE v 4.03), provided that any concomitant medication is given prior to initiation of

treatment with ceritinib. Exception to this criterion: patients with any grade of alopecia are allowed to enter the treatment.

7. Adequate organ function: the following laboratory criteria have been met:
  - Absolute neutrophil count (ANC)  $\geq 1.5 \times 10^9/L$
  - Hemoglobin (Hgb)  $\geq 8$  g/dL
  - Platelets  $\geq 75 \times 10^9/L$
  - Serum creatinine  $< 1.5$  mg/dL and /or calculated creatinine clearance (using Cockcroft-Gault formula)  $\geq 30$  mL/min
  - Total bilirubin  $\leq 1.5$  x upper limit of normal (ULN), except for patients with Gilbert's syndrome who may be included if total bilirubin  $\leq 3.0$  x ULN or direct bilirubin  $\leq 1.5$  x ULN
  - Aspartate transaminase (AST)  $< 2.0$  x ULN, except for patients with liver metastasis, who are only included if AST  $< 3$  x ULN; alanine transaminase (ALT)  $< 2.0$  x ULN, except for patients with liver metastasis, who are only included if ALT  $< 3$  x ULN
  - Alkaline phosphatase (ALP)  $\leq 5.0$  x ULN
  - Fasting plasma glucose  $\leq 175$  mg/dL ( $\leq 9.8$  mmol/L)
  - Serum amylase  $\leq 2$  x ULN
  - Serum lipase  $\leq$  ULN
8. Patient must have the following laboratory values or have the following laboratory values corrected with supplements to be above the lower limit of normal before the first dose of ceritinib:
  - Potassium
  - Magnesium
  - Phosphorus

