##### General guidelines for dose modifications

- For grade 1 and tolerable grade 2 treatment-related toxicities, patients are encouraged to continue at the current dose of study treatment. For intolerable grade 2 treatment-related toxicities, dosing should be interrupted until resolution to grade 1 or lower followed by dose reduction to the next dose level.
- For grade 3 or grade 4 treatment-related toxicity that is not considered by the investigator to be life-threatening, patients should interrupt study treatment until resolution to grade 1 or lower; then study treatment may continue following a dose reduction to the next dose level, if, in the opinion of the Investigator, the patient continues to experience clinical benefit. For any grade 3 or 4 treatment-related toxicity that is considered by the investigator to be life-threatening, permanently discontinue study treatment.

More detailed ceritinib dose modification guidelines are described in Section 4.3.1 respectively for selected toxicities.

All dose modifications, interruptions or discontinuations must be based on the worst preceding toxicity as graded by the NCI Clinical Toxicity Criteria version 4.03.

Patients whose treatment is interrupted or permanently discontinued due to an AE must be followed until resolution or stabilization of the event. Patients requiring interruptions greater than 1 cycle (28 days)

should be discontinued from ceritinib treatment unless the treating physician and Principle investigator agree that the patient should resume treatment.

All patients will be followed for safety until 30 days after the last dose of ceritinib.

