**Table 4-3 Criteria for interruption and re-initiation of Ceritinib treatment**

Worst toxicity (CTCAE 4.03 Grade)*	Dose Modifications for Ceritinib
HEMATOLOGICAL	
Neutropenia (ANC)	
Grade 1 (ANC < LLN - $1.5 \times 10^9/L$ )	Maintain dose level
Grade 2 (ANC < 1.5 and $\geq 1.0 \times 10^9/L$ )	Maintain dose level
Grade 3 (ANC < 1.0 and $\geq 0.5 \times 10^9/L$ )	Omit dose until resolved to $\leq$ Grade 2, then: If resolved in $\leq 7$ days, then maintain dose level If resolved in $> 7$ days, then $\downarrow$ 1 dose level
Grade 4 (ANC < $0.5 \times 10^9/L$ )	Omit dose until resolved to $\leq$ Grade 2, then: If resolved in $\leq 7$ days, then maintain dose level If resolved in $> 7$ days, then $\downarrow$ 1 dose level
Febrile neutropenia (ANC < $1.0 \times 10^9/L$ , with a single temperature of $\geq 38.3$ °C or a sustained temperature of $\geq 38$ °C for more than one hour )	Omit dose until clinically resolved and neutropenia $\leq$ Grade 2, then $\downarrow$ 1 dose level

Worst toxicity (CTCAE 4.03 Grade)*	Dose Modifications for Ceritinib
Thrombocytopenia	
Grade 1 (PLT < LLN - 75 x 10  /L)	Maintain dose level
Grade 2 (PLT < 75 and ≥ 50 x 10  /L)	Maintain dose level
Grade 3 (PLT < 50 and ≥ 25 x 10  /L)	Omit dose until resolved to ≤ Grade 2, then: If resolved in ≤ 7 days, then maintain dose level If resolved in > 7 days, then ↓ 1 dose level
Grade 4 (PLT < 25 x 10  /L)	Omit dose until resolved to ≤ Grade 2, then ↓ 1 dose level
HEPATIC	
alkaline phosphatase and/or Gamma-glutamyl transpeptidase (GGT)	
Isolated elevations of any grade	Maintain dose level
Total Bilirubin** (for patients with Gilbert Syndrome these dose modifications apply to changes in direct (conjugated) bilirubin only)	
Grade 1 (> ULN and ≤ 1.5 x ULN)	Maintain dose level with liver function test (LFTs)*** monitored as per protocol
Grade 2 (> 1.5 and ≤ 3.0 x ULN) with ALT or AST ≤ 3.0 x ULN	Omit dose until resolved to ≤ Grade 1, then: If resolved in ≤ 7 days, then maintain dose level If resolved in > 7 days, then ↓ 1 dose level
Grade 3 (> 3.0 and ≤ 10.0 x ULN) with ALT or AST ≤ 3.0 x ULN	Omit dose until resolved to ≤ Grade 1, then: If resolved in ≤ 7 days, ↓ 1 dose level If resolved in > 7 days discontinue patient from ceritinib
Grade 4 (> 10.0 x ULN)	Permanently discontinue patient from ceritinib
AST or ALT	

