Grade 1 (> ULN and ≤ 3.0 x ULN)	Maintain dose level with LFTs*** monitored per protocol
Grade 2 (> 3.0 and ≤ 5.0 x ULN) without total bilirubin elevation to > 1.5 x ULN	Omit dose until resolved to ≤ Grade 1, then If resolved in ≤ 7 days, then maintain dose level If resolved in > 7 days, then ↓ 1 dose level
Grade 3 (> 5.0 and ≤ 20.0 x ULN) without total bilirubin elevation to > 1.5 x ULN	Omit dose until resolved to ≤ Grade 1, then If resolved in ≤ 7 days, then maintain dose level If resolved in > 7 days, then ↓ 1 dose level
Grade 4 (> 20.0 x ULN) without bilirubin elevation to > 2.0 x ULN	Omit dose until resolved to ≤ Grade 1, then ↓ 1 dose level
AST or ALT and concurrent Total Bilirubin	
AST or ALT > 3.0 x ULN with total bilirubin > 2.0 x ULN in the absence of cholestasis or hemolysis	Permanently discontinue patient from ceritinib

Worst toxicity (CTCAE 4.03 Grade)*	Dose Modifications for Ceritinib
RENAL	
Serum creatinine	
Grade 1 (>1 and ≤1.5 x baseline; > ULN and ≤1.5 x ULN)	Maintain dose level
Grade 2 (>1.5 and ≤3.0 x baseline; >1.5 and ≤3.0 x ULN)	Omit dose until resolved to ≤ Grade 1, then: If resolved in ≤ 7 days, then maintain dose level If resolved in > 7 days, then ↓ 1 dose level
Grade 3 (>3.0 x baseline; >3.0 and ≤6.0 x ULN)	Omit dose until resolved to ≤ Grade 1, then ↓ 1 dose level
Grade 4 (> 6.0 x ULN)	Permanently discontinue patient from ceritinib
GASTROINTESTINAL	
Diarrhea****	
Grade 1 (despite maximal anti-diarrheal medication)	Maintain dose level but adjust anti-diarrhea treatment (may change anti-diarrhea treatment)
Grade 2 (despite maximal anti-diarrheal medication)	Omit dose until resolved to ≤ Grade 1, then maintain dose level. If diarrhea returns as ≥ Grade 2, then suspend dose until resolved to ≤ Grade 1, then ↓ 1 dose level
Grade 3 (despite maximal anti-diarrheal medication)	Omit dose until resolved to ≤ Grade 1, then ↓ 1 dose level
Grade 4 (despite maximal anti-diarrheal medication)	Omit dose until resolved to ≤ Grade 1, then ↓ 1 dose level
Nausea*****	
Grade 1 (despite standard anti-emetics)	Maintain dose level but adjust anti-emetic treatment
Grade 2 (despite standard anti-emetics)	Maintain dose level but adjust anti-emetic treatment
Grade 3 (despite standard anti-emetics)	Omit dose until resolved to ≤ Grade 1, then ↓ 1 dose level
Vomiting*****	
Grade 1 (despite standard anti-emetics)	Maintain dose level but adjust anti-emetic treatment

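### Table 4-3: with exactly one of ALT and AST above 3.0 x ULN, bilirubin above 2.0 and up to 10.0 x ULN, and neither cholestasis nor hemolysis, a restart row and the permanent-stop row both apply, and nothing ranks them

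*Combined protocol and SAP*

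**What the plan says.** The hepatic part of Table 4-3 (Section 4.3.1) has bilirubin rows, AST/ALT rows and one combined row.

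- **Bilirubin Grade 2:** "Grade 2 (> 1.5 and ≤ 3.0 x ULN) with ALT or AST ≤ 3.0 x ULN". Hold until Grade 1 or better. Restart at the same dose if this takes 7 days or less, and one level lower if it takes longer.
- **Bilirubin Grade 3:** "Grade 3 (> 3.0 and ≤ 10.0 x ULN) with ALT or AST ≤ 3.0 x ULN". Hold. Restart one level lower if resolved within 7 days; otherwise, "If resolved in > 7 days discontinue patient from ceritinib".
- **Combined row, under its own heading:** "AST or ALT > 3.0 x ULN with total bilirubin > 2.0 x ULN in the absence of cholestasis or hemolysis". Permanent discontinuation.

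The Total Bilirubin heading carries a qualifier: "for patients with Gilbert Syndrome these dose modifications apply to changes in direct (conjugated) bilirubin only". The combined row carries none. Inclusion criterion 7 (Section 3.2) caps total bilirubin at 1.5 x ULN, "except for patients with Gilbert's syndrome who may be included if total bilirubin" is at most 3.0 x ULN or direct bilirubin is at most 1.5 x ULN.

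The nearest thing to a tie-breaker is in the general guidelines of Section 4.3, repeated in a footnote to the table: dose changes "must be based on the worst preceding toxicity as graded by the NCI Clinical Toxicity Criteria version 4.03".

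**The concern.** The enzyme clause in the bilirubin rows seems meant to keep those rows apart from the combined row. The word 'or' defeats that when ALT and AST fall on opposite sides of 3.0 x ULN. The same patient is then told both to hold and possibly restart, and never to restart.

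The stake is patient safety. A site that follows the bilirubin row could re-challenge a patient with concurrent enzyme and bilirubin elevation whom the combined row removes for good. Section 7.3.2 lists hepatotoxicity as an adverse event of special interest, so the instruction for this state should have one meaning.

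**Working it through.** There is no sample-size or power figure to reproduce. The check is a comparison of conditions.

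**Conditions, all in multiples of ULN (Table 4-3).** Let B be total bilirubin, and let min and max be the lower and higher of ALT and AST.

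- Restart row (bilirubin Grade 2 or 3, literal 'or'): 1.5 < B ≤ 10.0 and min ≤ 3.0.
- Stop row (combined): B > 2.0 and max > 3.0, with neither cholestasis nor hemolysis.
- Both met: min ≤ 3.0 < max and 2.0 < B ≤ 10.0, with neither cholestasis nor hemolysis.

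These conditions were run over a grid without cholestasis or hemolysis: ALT and AST from 0.5 to 25 x ULN, bilirubin from 0.5 to 15 x ULN. The overlap matched this region with 0 mismatches. If the bilirubin rows required both enzymes at or below 3.0 (max ≤ 3.0), the overlap would be 0.

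**Examples, with neither cholestasis nor hemolysis:**

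| ALT | AST | Bilirubin | Bilirubin row | Combined row | Higher grade |
|---|---|---|---|---|---|
| 4.5 | 2.5 | 2.5 | Grade 2, restart | stop | equal (2 and 2) |
| 4.5 | 2.5 | 4.0 | Grade 3, restart if resolved within 7 days | stop | bilirubin (3 against 2) |
| 6 | 2 | 2.5 | Grade 2, restart | stop | enzyme (3 against 2) |
| 6 | 4 | 2.5 | not met | stop | no conflict |
| 4 | 2 | 2.0 | Grade 2, restart | not met | no conflict |
| 4 | 2 | 11 | Grade 4, stop | stop | no conflict |

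**Does any other text settle it?**

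- The worst-toxicity rule works by CTCAE grade, and the combined row has no grade. In the first example the rule is silent. In the second it points to the bilirubin Grade 3 row, which allows restart. Only where the enzyme grade is higher, as in the third, does it point away from the bilirubin row.
- The general guidelines in Section 4.3 defer to Section 4.3.1 for selected toxicities.
- Section 4.3.2.2 and Table 4-4 set monitoring, not precedence.
- Footnote ** covers indirect-only bilirubin elevation and does not rank the rows.

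**Where the two rows differ.** Both withhold ceritinib at first, so they differ only on restart. For bilirubin above 3.0 x ULN they differ only if it resolves within 7 days, because both otherwise end treatment.

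**Number of patients.** The documents give no rate for this state. Section 1.3.1.2.1 reports grade 3 or 4 ALT in 21% and AST in 11% of phase I patients, but not the other enzyme and bilirubin at the same moment. With assumed per-patient rates and n = 18 + 15 = 33: 33 x 0 = 0; 33 x 0.01 = 0.33; 33 x 0.03 = 0.99.

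**Gilbert syndrome.** Take total bilirubin 2.5, direct 1.0, ALT 3.5 and AST 2.0. If total bilirubin counts, the combined row is met (3.5 > 3.0 and 2.5 > 2.0). If only direct bilirubin counts, it is not (1.0 < 2.0). A total of 2.5 is within the entry limit of 3.0, so such a patient could meet the stop row with bilirubin unchanged since baseline.

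**The case against.** The strongest reply is that the layout shows the intent. The AST/ALT rows carry matching bilirubin exclusions, for example "Grade 2 (> 3.0 and ≤ 5.0 x ULN) without total bilirubin elevation to > 1.5 x ULN". The combined row has its own heading and is the more specific instruction for the joint state. A column headed by worst toxicity can also be read as judging on the worse enzyme. Read that way throughout, the bilirubin rows need both enzymes at or below 3.0 and the overlap disappears. In addition, a permanent stop is terminal: a site obeying every row it meets never reaches the restart step. Section 4.3.2.2 also requires liver tests at least weekly.

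Most of this stands, and it is why the point is minor. Many clinicians would stop. But the intended reading has to be inferred: no sentence gives the combined row precedence, and the worst-toxicity rule can point the other way.

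A reader might infer that every hepatic row in play at least interrupts dosing. The documents do not support that. If 'or' is taken literally in the AST/ALT rows too, a lower enzyme above ULN and up to 3.0 x ULN also meets the Grade 1 row, which keeps the dose. In the first example AST 2.5 does so. Only the bilirubin and combined rows can be said to withhold ceritinib.

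**Conclusion.** The conflict is real on the literal wording, and its limits are exact: one enzyme above 3.0 x ULN and the other not, bilirubin above 2.0 and up to 10.0 x ULN, and neither cholestasis nor hemolysis. It is a minor error in a safety instruction. It probably concerns 0 to 1 of 33 patients, a figure that rests wholly on the assumed rates of 0 to 3%.

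Two stronger readings go too far. A reader might infer that the plan intends re-challenge in this state; the separate combined heading suggests the opposite. A reader might also infer an effect on PFS, since Section 2.0 counts unacceptable toxicity as an event. With no rate in the documents and at most about one patient on the assumed rates, none can be shown. The sample-size calculation in Section 9.2 does not use these rows, so power is untouched.

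**What to change.** Add one line to Table 4-3: when the combined AST/ALT and total bilirubin row is met, it governs over every other hepatic row and ceritinib is permanently discontinued.

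In the same amendment, the sponsor should state whether the direct-bilirubin qualifier for Gilbert syndrome applies to the combined row. That is a clinical decision. Left open, the new line could remove a patient whose bilirubin has not changed since entry.

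Requiring both enzymes to be at or below 3.0 x ULN in the two bilirubin rows would also end the overlap. It would, however, change which patients outside the overlap meet those rows, so the precedence line is the smaller change.

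The cost is a short amendment with IRB approval (Section 11.6) and the sponsor's decision on Gilbert syndrome. No tests, visits or patients are added: the liver panel in Section 4.3.2.2 already fractionates bilirubin above 2.0 x ULN and monitors both total and direct bilirubin in Gilbert patients.

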### 4.3.2 Follow-up for toxicities

An unscheduled visit should be performed in all cases below where toxicity monitoring is recommended more frequently than defined by the schedule of assessments (table 5-1).

Ongoing SAEs at the final safety evaluation visit or the end of study treatment visit (whichever is later) should be followed until they improve becoming non serious events, stabilize, or return to baseline levels. Refer to Section 7.2 for SAE.

A summary of selected toxicity follow-up recommendations is listed in table 4-4. For full toxicity information and dosing adjustments please refer to Table 4-3.

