**Table 4-4 Follow-up recommendations for specific toxicities**

Toxicity	Follow-up evaluation*
Investigations (hematologic)	Febrile neutropenia, neutropenia or thrombocytopenia $\geq$ CTCAE Grade 3 Test weekly (or more frequently) until $\leq$ Grade 2 Subsequent monitoring must be performed every 3 weeks (or more frequently)
Investigations (hepatic)	Total ALT/AST/total bilirubin Grade 2: Test weekly (or more frequently) until $\leq$ Grade 1 Thereafter, continue to test every 2 weeks (or more frequently) for 2 cycles (8 weeks). If no recurrence of $\geq$ Grade 2 event, continue monitoring every cycle (4 weeks) Total ALT/AST/total bilirubin $\geq$ Grade 3: Test weekly (or more frequently) until $\leq$ Grade 1 Thereafter, continue to test every 2 weeks (or more frequently) for 4 cycles (16 weeks). If no recurrence of $\geq$ grade 2 event, continue monitoring every cycle (4 weeks) Discontinuation due to liver toxicity: Test weekly (or more frequently) until $\leq$ Grade 1 or stabilization
Investigations (renal)	Serum creatinine Grade 2: Test weekly (or more frequently) until Grade 1 Thereafter, test every cycle (4 weeks) Serum creatinine $\geq$ Grade 3: Test twice weekly (or more frequently) until $\leq$ Grade 1 Thereafter, test every cycle (4 weeks)
Investigations (Metabolic)	Hyperglycemia $\geq$ Grade 3 Test weekly (or more frequently) until Grade 1
Investigations (pancreatic)	Amylase/lipase $\geq$ Grade 3: Test weekly (or more frequently) until $\leq$ Grade 1. After resumption of dosing, continue to test weekly for one additional cycle (4 weeks). If no reoccurrence of $\geq$ Grade 2 event, continue monitoring every cycle (4 weeks).

**\*Note:** this table refers only to the evaluation schedule to monitor selected toxicities. Refer to [Table 4-3](#) for dose modifications required for applicable toxicities

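### Table 4-3 has no dosing row when ALT and AST are both >3.0 to ≤20.0 x ULN with total bilirubin >1.5 to ≤2.0 x ULN; in the grade 2 part the only fallback text leans toward continuing

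*Combined protocol and SAP*

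**What the plan says.** Table 4-3 (Section 4.3.1) sets the hepatic dosing rules in three blocks.

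- **Bilirubin.** The grade 2 row is "Grade 2 (> 1.5 and ≤ 3.0 x ULN) with ALT or AST ≤ 3.0 x ULN". The action is to hold until Grade 1 or lower, then resume the same dose if that took 7 days or less, or drop one level if longer. For patients with Gilbert syndrome this block applies to direct bilirubin only.
- **AST or ALT.** Grade 2 is "Grade 2 (> 3.0 and ≤ 5.0 x ULN) without total bilirubin elevation to > 1.5 x ULN" and grade 3 is "Grade 3 (> 5.0 and ≤ 20.0 x ULN) without total bilirubin elevation to > 1.5 x ULN". Both carry the same hold and 7-day rule. The grade 4 row (>20 x ULN) applies up to bilirubin 2.0 x ULN and means hold, then reduce.
- **Combined.** "AST or ALT > 3.0 x ULN with total bilirubin > 2.0 x ULN in the absence of cholestasis or hemolysis" means permanent discontinuation.

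The general guidelines in Section 4.3 state: "For grade 1 and tolerable grade 2 treatment-related toxicities, patients are encouraged to continue at the current dose of study treatment". Intolerable grade 2 events are interrupted and then reduced. Treatment-related grade 3 or 4 events that are not life-threatening are interrupted until Grade 1 or lower, and "then study treatment may continue following a dose reduction to the next dose level" if the investigator sees continued benefit.

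Section 4.3.2 points back to the table: "For full toxicity information and dosing adjustments please refer to Table 4-3". The note under Table 4-4 says "this table refers only to the evaluation schedule to monitor selected toxicities".

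**The concern.** The three blocks use different bilirubin limits: 1.5 x ULN in the grade 2 and 3 enzyme rows, 2.0 x ULN in the combined row. The grade 2 bilirubin row would bridge the interval, but only while ALT or AST is at or below 3.0 x ULN. When both enzymes are above that, nothing in the table applies.

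The gap lies just below the threshold for permanent discontinuation, and it concerns hepatotoxicity, which Section 7.3.2 lists as an adverse event of special interest. At stake are different handling of similar patients and a possible missed dose hold.

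**Working it through.** No arithmetic in the plan needs reproducing. The check is whether each combination of values meets the entry condition of some row.

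**Inputs.** All hepatic rows of Table 4-3 and its bilirubin footnote. The enzyme rows are read on the worse enzyme, *ALT or AST* in the bilirubin rows is read literally (either one), and cholestasis and hemolysis are assumed absent.

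**Step 1: grid.** ALT in 4 bands (≤3, >3–5, >5–20, >20 x ULN), AST in the same 4, and bilirubin in 5 (≤1.5, >1.5–2.0, >2.0–3.0, >3–10, >10 x ULN): 4 × 4 × 5 = 80 cells.

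**Step 2: unmatched cells.** Four of the 80 match no row: ALT in 2 bands (>3–5, >5–20) × AST in the same 2 × bilirubin in 1 band (>1.5–2.0) = 4. In one of them (both enzymes >3–5) the worse enzyme is grade 2; in the other three it is grade 3. These counts locate the gap. They are not frequencies.

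**Step 3: example inside the gap.** ALT 4, AST 4, bilirubin 1.8 x ULN:
- Bilirubin grade 1 fails, because 1.8 > 1.5.
- Bilirubin grade 2 fails, because neither enzyme is ≤3.0.
- AST/ALT grade 2 fails, because bilirubin is above 1.5.
- The combined row fails, because 1.8 is not above 2.0.
- The bilirubin footnote covers only grade 3 or 4 hyperbilirubinemia.

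**Step 4: neighbouring cases.**

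| ALT / AST (x ULN) | Bilirubin (x ULN) | Row | Action |
|---|---|---|---|
| 4 / 4 | ≤1.5 | AST/ALT grade 2 | Hold; same dose if ≤7 days, else reduce |
| ≤3 / ≤3 | 1.8 | Bilirubin grade 2 | Hold; same dose if ≤7 days, else reduce |
| 4 / 2 | 1.8 | Bilirubin grade 2 (literal *or*) | Hold; same dose if ≤7 days, else reduce |
| **4 / 4** | **1.8** | **none** | **none in table** |
| **10 / 10** | **1.8** | **none** | **none in table** |
| 25 / 4 | 1.8 | AST/ALT grade 4 | Hold, then reduce |
| 4 / 4 | just above 2.0 | Combined | Permanent discontinuation |

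The grade 4 enzyme row uses the 2.0 limit and meets the combined row without a break. Only grades 2 and 3 leave the interval open.

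**Step 5: what text remains.** Table 4-4 and Section 4.3.2.2 set monitoring only, so Section 4.3 is the only other dosing text.
- *Worse enzyme >3 to ≤5:* continuing is encouraged if the event is treatment-related and tolerable; interruption and reduction follow only if it is intolerable. That is less cautious than the table's action for either abnormality alone.
- *Worse enzyme >5 to ≤20:* treatment-related, non-life-threatening events are interrupted and then reduced. A cautious action already exists.

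**Step 6: sensitivity to the literal *or*.** If the grade 2 bilirubin row needs both enzymes ≤3.0, the cells with one enzyme ≤3 and the other >3 to ≤20 also fall out: 2 × 1 × 2 = 4 more, or 8 of 80. The gap described here lies wholly inside that larger one.

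**The case against.** The strongest reply is that no investigator would treat two simultaneous findings, each requiring a hold, as milder than one. Section 4.3 itself defers to 4.3.1 for detail, and 4.3.1 holds the drug for each component and stops it just above the band. On that view the natural reading is at least to hold. The same bullet in 4.3 interrupts intolerable grade 2 events, Section 4.1.2 allows discontinuation at the investigator's discretion, and Section 4.3.2.2 requires weekly liver tests after any grade 2 rise.

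Much of this stands. Using 4.3 as the fallback is an inference, and these safeguards limit the harm. They do not supply the missing rule: a hold for the combination is written nowhere, while the table states an action on every side of it.

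A reader might infer more than the documents support:
- **That the protocol tells investigators to keep dosing.** It does not. The general rule depends on relatedness and tolerability, and discretion to stop remains.
- **That the grade 3 part is equally exposed.** It is not, because 4.3 already gives interruption and reduction there.
- **That the quoted enzyme rates size the problem.** Grade 3–4 ALT is given as 15.5% (Section 7.1.4) and 21% (Section 1.3.1.2.1). Those figures say nothing about grade 2 rises with bilirubin >1.5 to ≤2.0 x ULN.

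**Conclusion.** The gap is real and exactly bounded: ALT and AST both >3.0 to ≤20.0 x ULN with total bilirubin >1.5 to ≤2.0 x ULN. It has consequences only where the worse enzyme is ≤5.0 x ULN. There the written rules, with 4.3 as the inferred fallback, give a less cautious action for the combined abnormality than for either one alone. Where the worse enzyme is above 5.0 x ULN, it is a missing row and no more.

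The frequency is unknown and cannot be derived from the documents. The combination cannot be present at entry, since Section 3.2 requires AST and ALT below 2.0 x ULN, or below 3 x ULN with liver metastasis. The primary analysis is not affected.

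The bounds rest on the literal *or* in the bilirubin rows; the stricter reading only widens the gap. The point should be corrected because the edit is small and the event is one of special interest, not because harm has been shown.

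**What to change.** Add one row to Table 4-3, confined to the gap:

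> *ALT and AST both >3.0 to ≤20.0 x ULN with total bilirubin >1.5 to ≤2.0 x ULN, no cholestasis or hemolysis (direct bilirubin only in Gilbert syndrome):* hold ceritinib until AST/ALT and bilirubin are both Grade 1 or lower. *Worse enzyme ≤5.0 x ULN:* if resolved in ≤7 days, resume the same dose; if >7 days, reduce one level. *Worse enzyme >5.0 x ULN:* reduce one level.

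The first branch copies the 7-day rule shared by both grade 2 component rows. The second copies what 4.3 already requires. Three choices matter:
- **Leave cells already covered by the grade 2 bilirubin row alone.** A row triggered by either enzyme would override that row in 4 cells (one enzyme ≤3, the other >3 to ≤20).
- **Keep the Gilbert exception.** Such patients may enter with total bilirubin up to 3.0 x ULN and might never resolve on that measure. Under 4.3, interruptions beyond 28 days should end treatment unless the treating physician and the principal investigator agree otherwise.
- **Do not simply raise the grade 3 bilirubin limit to 2.0.** ALT and AST of 10 x ULN with bilirubin 1.8 x ULN could then resume at full dose after ≤7 days, which is laxer than 4.3.

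The row fills the 4 unmatched cells and overlaps no existing row. Cases with cholestasis or hemolysis are not addressed by it.

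The cost is a one-row edit, occasional extra dose holds and, in some patients, use of one of the two reduction steps (450 to 300 to 150 mg).
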